14.2.2 Stage 3A in Patients with CMML

The purpose of Stage 3A is to evaluate the clinical benefit derived from individual components, or variations thereof, of the MDS/MPN 2015 criteria that may allow for a prospective definition of a primary efficacy endpoint, that will provide the primary evidence of efficacy for regulatory decision-making in the planned confirmatory cohort (Stage 3B; to be added under the auspices of separate amendment). Individual evaluations will be performed for each of the two CMML cohorts in Stage 3A.

Approximately 20 patients with CMML may be enrolled in each of the two cohorts in Stage 3A to ensure a sufficient number of patients with specific baseline disease characteristics are enrolled to reject a meaningless rate of clinical activity in subsets of interest. (For our purposes, a meaningless rate will be taken to mean that there are no responders, using the definitions below, in the sample for each of the following subsets.) No formal stratification will be performed; however approximately 8-10 patients with baseline splenomegaly (defined as ≥ 5 cm below the left costal margin) and approximately 8-10 patients who are transfusion-dependent at baseline (receipt of at least 4 transfusions within 8 weeks before the first tagraxofusp dose) will be included in each 20-patient cohort. This intended enrollment distribution may be adjusted, depending on the actual prevalence of splenomegaly and transfusion-dependence seen in the general patient population as the study continues to enroll.

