It is underscored that the consensus definition of a CR bone marrow is to be used only in those patients in which all other criteria are met, including resolution of leukoerythroblastosis. It should also be noted that it was a particularly difficult task for the working group to reach a consensus regarding what represents a complete histologic remission.
- 3 Immature myeloid cells constitute blasts + promyelocytes + myelocytes + metamyelocytes + nucleated red blood cells. In splenectomized patients, < 5% immature myeloid cells is allowed.
- 4 See above for definitions of anemia response, spleen response, and progressive disease. Increase in the severity of anemia constitutes the occurrence of new transfusion dependency or a ≥ 20 g/L decrease in hemoglobin level from pretreatment baseline that lasts for at least 12 weeks. Increase in severity of thrombocytopenia or neutropenia is defined as a 2-grade decline, from pretreatment baseline, in platelet count or absolute neutrophil count, according to the CTCAE version 4.03. In addition, assignment to CI requires a minimum platelet count of $\geq 25 \times 10^9$ /L and absolute neutrophil count of $\geq 0.5 \times 10^9$ /L.
- 5 Applicable only to patients with baseline hemoglobin of < 100g/L. In patients not meeting the strict criteria for transfusion dependency at the time of study enrollment (see as follows), but have received transfusions within the previous month, the pretransfusion hemoglobin level should be used as the baseline.
- 6 Transfusion dependency before study enrollment is defined as transfusions of at least 6 units of pRBCs in the 12 weeks prior to study enrollment, for a hemoglobin level of < 85 g/L, in the absence of bleeding or treatment-induced anemia. In addition, the most recent transfusion episode must have occurred in the 28 days prior to study enrollment. Response in transfusion-dependent patients requires absence of any pRBC transfusions during any consecutive “rolling” 12-week interval during the treatment phase, capped by a hemoglobin level of ≥ 85 g/L.
- 7 In splenectomized patients, palpable hepatomegaly is substituted with the same measurement strategy.
- 8 Spleen or liver responses must be confirmed by imaging studies where a $\geq 35\%$ reduction in spleen volume, as assessed by MRI or CT, is required. Furthermore, a $\geq 35\%$ volume reduction in the spleen or liver, by MRI or CT, constitutes a response regardless of what is reported with physical examination.

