Bone Marrow CR ⁽²⁾	Bone marrow $\leq 5\%$ myeloblasts and decrease by $\geq 50\%$ over pretreatment ² Peripheral blood: If hematologic improvement responses, they will be noted in addition to marrow CR ²
Stable disease	Failure to achieve at least PR, but no evidence of progression for > 8 weeks
Failure	Death during treatment or disease progression characterized by worsening of cytopenias, increase in percentage of bone marrow blasts or progression to a more advanced MDS FAB subtype than pretreatment
Relapse after CR or PR	At least 1 of the following: Return to pretreatment bone marrow blast percentage Decrement of $\geq 50\%$ from maximum remission/response levels in granulocytes or platelets Reduction in Hemoglobin concentration by $\geq 1.5\text{ g/dL}$ or transfusion dependence
Cytogenetic response	Complete: Disappearance of the chromosomal abnormality without appearance of new ones Partial: At least 50% reduction of the chromosomal abnormality
Disease progression	For patients with: Less than 5% blasts: $\geq 50\%$ increase in blasts to $> 5\%$ blasts 5-10% blasts: $\geq 50\%$ increase to $> 10\%$ blasts 10-20% blasts: $\geq 50\%$ increase to $> 20\%$ blasts 20-30% blasts: $\geq 50\%$ increase to $> 30\%$ blasts Any of the following: At least 50% decrement from maximum remission/response in granulocytes or platelets Reduction in Hemoglobin by $\geq 2\text{ g/dL}$ Transfusion dependence
Survival	Endpoints: Overall: death from any cause Event free: failure or death from any cause PFS: disease progression or death from MDS DFS: time to relapse Cause-specific death: death related to MDS

Adapted from Cheson, et al. Blood 2006; 108(2):419-25.

Deletions to the IWG response criteria are not shown. To convert hemoglobin from g/dL to g/L, multiply g/dL by 10.

MDS: myelodysplastic syndromes. Hgb: hemoglobin. CR: complete remission. HI: Hematologic improvement. PR: partial remission. FAB: French-American-British. AML: Acute myeloid leukemia. PFS: Progression-free survival. DFS: Disease-free survival.

1 Dysplastic changes should consider the normal range of dysplastic changes (modification) (Ramos 1999)

2 Modification to IWG response criteria

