- 3 Given the current lack of a validated tool to assess complete resolution of symptoms in MDS/MPN, “CR with resolution of symptoms” (a complete resolution of disease-related symptoms as noted by the MPN-SAF TSS in presence of CR) will be a provisional category of disease response.
- 4 Loss of cytogenetic burden of disease (via FISH or classic karyotyping) known to adversely affect prognosis is required to reach complete cytogenetic remission. Decrease in the cytogenetic burden of disease must be by $\geq 50\%$ (via FISH or classic karyotyping) to be indicative of a partial cytogenetic response. Given variability of fluorescent probes used in FISH, cytogenetic normalization via FISH will depend on the performance characteristics of the specific probes used.
- 5 Resolution of abnormal peripheral blood counts must persist for at least 2 separate analyses over at least 8 weeks. In the case of proliferative MDS/MPN, CR will include resolution of thrombocytosis to a normal platelet count ($150-450 \times 10^9/L$) and resolution of leukocytosis to WBC $\leq 10 \times 10^9$ cells/L but $\geq 1.5 \times 10^9/L$. Hemoglobin should be maintained > 11 g/dL and platelets $\geq 100 \times 10^9/L$ without the support of transfusions. Clinical benefit may occur when these changes occur in absence of other changes required for CR or marrow response. Platelet and packed red blood cell TI would be considered for clinical benefit, and duration of TI should be monitored. Reduction in myeloid precursors (promyelocytes, myelocytes, metamyelocytes, nucleated red blood cells) to less than appreciable levels ($\leq 2-3\%$) and/or $1 \times 10^9/L$ monocytosis in the absence of infection, cytokine treatment, or other reactive causes.
- 6 MPN-SAF TSS validation among patients with MDS/MPN is currently under way (R.A. Mesa, personal communication, 2014).

Criteria for measurement of disease progression in adult MDS/MPN

Combination of 2 major criteria, 1 major and 2 minor criteria, or 3 minor criteria from list

Major criteria

- Increase in blast count¹
 - < 5% blasts: ≥ 50% increase and to > 5% blasts
 - 5-10% blasts: ≥ 50% increase and to > 10% blasts
 - 10-20% blasts: ≥ 50% increase and to > 20% blasts
 - 20-30% blasts: ≥ 50% increase and to > 30% blasts²
- Evidence of cytogenetic evolution³
 - Appearance of a previously present or new cytogenetic abnormality in complete cytogenetic remission via FISH or classic karyotyping.

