 - Increase in cytogenetic burden of disease by ≥ 50% in partial cytogenetic remission via FISH or classic karyotyping.
- New extramedullary disease.
 - Worsening splenomegaly:

Progressive splenomegaly that is defined by IWG-MRT: the appearance of a previously absent splenomegaly that is palpable at > 5 cm below the left costal margin or a minimum 100% increase in palpable distance for baseline splenomegaly of 5-10 cm or a minimum 50% increase in palpable distance for baseline splenomegaly of > 10 cm

Extramedullary disease outside of the spleen to include new/worsening hepatomegaly, granulocytic sarcoma, skin lesions, etc.

Minor criteria

- Transfusion dependence⁴
- Significant loss of maximal response on cytopenias ≥ 50% decrement from maximum remission/response in granulocytes or platelets
- Reduction in Hgb by ≥ 1.5 g/dL from best response or from baseline as noted on complete blood count
- Increasing symptoms as noted by increase in ≥ 50% as per the MPN-SAF TSS⁵
- Evidence of clonal evolution (molecular)⁶

1 Blasts as measured from the bone marrow.

2 Patients with development of acute myeloid leukemia from MDS/MPN; 20-30% blasts may be allowed on some clinical trials for patients with MDS/MPN.

3 Increase in cytogenetic burden of disease by ≥ 50% (via FISH or classic karyotyping). Given variability of fluorescent probes used in FISH, cytogenetic normalization via FISH will depend on specific probes used.

4 Transfusion dependency is defined by a history of at least 2 units of red blood cell transfusions in the past month for a hemoglobin level < 8.5 g/dL that was not associated with clinically overt bleeding. Cytopenia resulting from therapy should not be considered in assessment of progression.

5 MPN-SAF TSS validation among patients with MDS/MPN is currently under way (R.A. Mesa, personal communication, 2014).

6 The identification of new abnormalities using single nucleotide polymorphism arrays or sequencing or a clearly significant increase in mutational burden of a previously detected abnormality. Precise criteria for defining new abnormalities and what exactly constitutes a significant increase in mutational burden are open to interpretation; we suggest that this criterion should be used conservatively based on current evidence.

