CMML patients will be classified as “dependent” or “independent” at baseline within each category of platelets, packed red blood cells (pRBC), and both (i.e., receiving both platelets and pRBC) if they received transfusions of at least 4 units in the 8 weeks prior to the study enrollment. Transfusion independence for CMML will be defined as patients who experience at least a 8 week period during any point on treatment with no transfusion of that type required.

Secondary Efficacy Endpoints

The secondary efficacy endpoints are DOR, PFS, OS, and duration of follow-up.

Duration of objective response is defined as the time from when criteria are first met for CR or PR until the date that the criteria for relapse is met. Progression-free survival is defined as the time from the date of first infusion of tagraxofusp to the date of PD or death from any cause. Overall survival is defined as the time from the date of first infusion of tagraxofusp to the date of death from any cause.

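### In Stage 3A, transfusion dependence counts toward progression with no baseline reference, so a patient who enters transfused and stays so is called PD on one fewer minor criterion

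*Protocol*

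**What the plan says.** For Stage 3A, Protocol 18.1 Table 8 (SAP Table 8-4) sets the progression rule as "Combination of 2 major criteria, 1 major and 2 minor criteria, or 3 minor criteria from list". There are three major headings (blast increase, cytogenetic evolution, new extramedullary disease) and five minor criteria.

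Four of the minor criteria are changes: loss of response in granulocytes or platelets, a hemoglobin fall, worsening symptoms, and clonal evolution. The hemoglobin item names its reference: "from best response or from baseline as noted on complete blood count". The fifth is transfusion dependence. Footnote 4 reads "Transfusion dependency is defined by a history of at least 2 units of red blood cell transfusions in the past month", for hemoglobin below 8.5 g/dL without overt bleeding. Its only further limit is "Cytopenia resulting from therapy should not be considered in assessment of progression".

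Protocol 14.2.2 plans, in each cohort of about 20, "approximately 8-10 patients who are transfusion-dependent at baseline (receipt of at least 4 transfusions within 8 weeks before the first tagraxofusp dose". SAP 1.2.5.1 classifies CMML patients as dependent at baseline, for platelets, red cells or both, "if they received transfusions of at least 4 units in the 8 weeks prior to the study enrollment".

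For Stage 2, Protocol Table 7 (SAP Table 8-3) lists transfusion dependence among items of which any one is named as progression. It stands beside "At least 50% decrement from maximum remission/response in granulocytes or platelets" and a hemoglobin fall, and has no baseline reference and no unit threshold.

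**The concern.** A progression rule should register worsening. As written, this item also registers an unchanged transfusion need that was there before the first dose. Footnote 4 exempts cytopenia caused by treatment but not dependence caused by the disease before treatment. The patients affected belong largely to a subset that Stage 3A deliberately enrolls.

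PD is a PFS event (SAP 4.3.3) and a best-response category (SAP 4.3.1). Its absence is a condition for clinical benefit (Table 8). Stable disease is the residual category in Stage 3A, so the PD boundary decides who is stable and who has progressed.

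**Working it through.** **1. The plan's own figure.** The only computed design figure for this subset is the chance of at least one responder among 10 patients at a true rate of 0.15 (Protocol 14.2.2). 1 - 0.85^10 = 0.803, which matches the stated 80%. It is not in dispute. The progression rule has no stated figure.

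**2. What remains to be met.** For a patient who meets footnote 4 at entry and stays transfused:

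| Route to PD | As written | If unchanged dependence did not count |
|---|---|---|
| Major only | 2 major | 2 major |
| Mixed | 1 major + 1 other minor | 1 major + 2 other minor |
| Minor only | 2 other minor | 3 other minor |

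**3. Enumeration.** The other 3 major and 4 minor criteria give 2^7 = 128 met/not-met patterns.
- As written: at least 2 major, 4 × 16 = 64; exactly 1 major with at least 1 minor, 3 × 15 = 45; no major with at least 2 minor, 11. Total 120.
- Unchanged dependence not counted: 64; 1 major with at least 2 minor, 3 × 11 = 33; no major with at least 3 minor, 5. Total 102.

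So 18 patterns are PD only because of the carried-in criterion. The patterns are not equally likely, so this shows direction and not size.

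**4. Look-back.** The first post-baseline assessment is at the end of Cycle 1, Day 21 ± 3, that is Day 18 to 24. If a month is taken as 30 days (assumption), the window reaches 30 - 24 = 6 to 30 - 18 = 12 days before the first dose. Pre-treatment transfusions can therefore count toward on-study progression.

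**5. Illustration of size.** The documents give no frequency for any criterion. Assume that each major criterion is met with probability a and each other minor with probability b at one assessment, all independent. Let M be the number of major and m the number of other minor criteria met.
- As written: P(M≥2) + P(M=1)·P(m≥1) + P(M=0)·P(m≥2).
- Not counted: P(M≥2) + P(M=1)·P(m≥2) + P(M=0)·P(m≥3).

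For a = 0.10, b = 0.20: 0.028 + 0.243 × 0.5904 + 0.729 × 0.1808 = 0.303 as written, against 0.028 + 0.243 × 0.1808 + 0.729 × 0.0272 = 0.092.

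| a / b (assumed) | PD as written | PD if not counted |
|---|---|---|
| 0.05 / 0.10 | 9.9% | 1.8% |
| 0.05 / 0.20 | 24.2% | 5.5% |
| 0.10 / 0.10 | 15.0% | 4.3% |
| 0.10 / 0.20 | 30.3% | 9.2% |
| 0.10 / 0.30 | 46.7% | 17.4% |
| 0.15 / 0.25 | 44.4% | 17.7% |

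The ratio runs from about 2.5 to 5.6 (unrounded values).

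**6. Which endpoints can move.**
- PFS, and stable versus progressive disease: yes, since PD enters directly.
- Clinical benefit: yes, for platelet, neutrophil, spleen or symptom benefit in a patient who stays transfused.
- ORR: no. It counts CR and PR only.
- Objective duration of response: no. It starts at CR or PR. CR needs hemoglobin of at least 11 g/dL held without transfusion, and PR needs normalized peripheral counts. Dependence after such a response is new.
- Conversion to transfusion independence: no. A converter drops out of a one-month look-back, and the SAP 4.3.7 summary is not conditioned on absence of PD.

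**7. Definitions side by side.** Protocol 14.2.2 counts 4 transfusions in 8 weeks before first dose. SAP 1.2.5.1 counts 4 units in 8 weeks before enrollment, and platelets can qualify. Footnote 4 counts 2 red-cell units in a month with a hemoglobin threshold. The three groups overlap but need not coincide.

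**The case against.** The strongest reply is that progression implies change. Any hematologist would discount a stable need, and the table is adopted from published consensus criteria. The text does not say so, however, and leaving it to each assessor invites inconsistent PD calls between sites. Published wording is no bar either: the sponsor already removed a provisional CR category and added stable disease.

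It is also fair that dependence alone is never PD in Stage 3A, that treatment-caused cytopenia is exempt, that the 8-10 per cohort was an adjustable intention and enrollment was not continued (SAP 5), and that the analyses are descriptive without type I error control (SAP 3.7). These points limit the consequence but leave the rule as it is.

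Some stronger readings are tempting but not supported:
- *Footnote 4 sets a lower bar than baseline dependence.* Two units a month is about 2 × 2 = 4 units in 8 weeks, so that patient is already dependent under the SAP. The gap appears only if the protocol's transfusions are counted as episodes.
- *The MF table shows the right progression wording.* The phrase "Increase in the severity of anemia constitutes the occurrence of new transfusion dependency" qualifies clinical improvement in MF. The MF progression row does not list transfusion dependence.
- *Every baseline-dependent Stage 2 patient has PD at once.* That is only a literal reading of Table 7. The table gives no unit threshold, its failure row describes progression through worsening cytopenias, and the number of such patients is not given.

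**Conclusion.** The point holds for Stage 3A. The progression rule counts a pre-existing state as if it were a change, which lowers the bar by one minor criterion for patients who enter transfused and remain so. The direction, toward earlier PD, follows from the text. The size does not: the percentages above rest wholly on assumed, independent probabilities at a single assessment. How many patients are affected is also unknown, because the baseline definitions do not match footnote 4 and enrollment ended early. A reader might infer that the primary response results or the transfusion-independence finding are compromised; the definitions of those endpoints do not support that. Stage 2 has the same omission, and one item may suffice there if the table is read literally.

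**What to change.** - In Protocol Tables 7 and 8 and SAP Tables 8-3 and 8-4, state that transfusion dependence counts toward progression only if it is new or worse than in the pre-treatment period.
- Define worsening for patients dependent at entry before database lock. Requiring simply that dependence was absent at baseline would go too far: such patients could then never meet the criterion, even if their need rose sharply.
- Reconcile the two baseline definitions (4 transfusions, 4 units) with footnote 4.
- Keep the investigator-assessed result as the main analysis; replacing it after enrollment has stopped would be a post-hoc endpoint change. List every PD that rests on this criterion in a baseline-transfused patient, and report PFS and best response under the clarified rule as a sensitivity analysis.

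The data should exist: CMML transfusions are recorded for 8 weeks before first dose (Protocol 11.3) and after first dose as concomitant therapy (Protocol 13.6). The cost is a small departure from the published wording and a little more analysis work. Some PD dates may move later.

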18.2 ECOG Performance Status

The ECOG performance status scale, with corresponding Karnofsky performance status score equivalents, is presented in [Table 9](#).

Table 9 Eastern Cooperative Oncology Group Performance Status Scale, with Equivalent Karnofsky Performance Status Scores

ECOG ¹		Karnofsky ²	
Score	Criterion	%	Criterion
0	Normal activity	100	Normal; no complaints; no evidence of disease
		90	Able to carry on normal activity; minor signs or symptoms of disease
1	Symptoms but ambulatory	80	Normal activity with effort; some signs or symptoms of disease
		70	Cares for self; unable to carry on normal activity or do active work
2	In bed < 50% of time	60	Requires occasional assistance but is able to care for most of his/her needs
		50	Requires considerable assistance and frequent medical care
3	In bed > 50% of time	40	Disabled, requires special care and assistance
		30	Severely disabled; hospitalization is indicated though death is not imminent
4	100% bedridden	20	Very sick; hospitalization is necessary
		10	Moribund; fatal processes progressing rapidly
5	Dead	0	Dead

18.3 CLS Management Guidance

Time of Presentation	CLS Sign/Symptom	Recommended Action	Tagraxofusp Dosing Management
Prior to first dose of tagraxofusp in Cycle 1	Serum albumin < 3.2 g/dL	Administer tagraxofusp when serum albumin \geq 3.2 g/dL.	
	Serum albumin < 3.5 g/dL	Administer 25g intravenous albumin (q12h or more frequently as practical) until serum albumin is \geq 3.5 g/dL AND not more than 0.5 g/dL lower than the value measured prior to dosing initiation of the current cycle.	
During tagraxofusp dosing	Δ predose body weight that is increased by \geq 1.5 kg over the previous day's predose weight	
Administer 25g intravenous albumin (q12h or more frequently as practical), and manage fluid status as indicated clinically (e.g., generally with intravenous fluids and vasopressors if hypotensive and with diuretics if normotensive or hypertensive), until body weight increase has resolved (i.e. the increase is no longer \geq 1.5 kg greater than the previous day's predose weight).
 
Administer 25g intravenous albumin (q12h, or more frequently as practical) until serum albumin is \geq 3.5 g/dL.
	
Administer 25g intravenous albumin (q12h or more frequently as practical), and manage fluid status as indicated clinically (e.g., generally with intravenous fluids and vasopressors if hypotensive and with diuretics if normotensive or hypertensive), until body weight increase has resolved (i.e. the increase is no longer \geq 1.5 kg greater than the previous day's predose weight).
 
Administer 25g intravenous albumin (q12h, or more frequently as practical) until serum albumin is \geq 3.5 g/dL.

	Edema, fluid overload and/or hypotension	
Administer 1 mg/kg of methylprednisolone (or an equivalent) per day, until resolution of CLS sign/symptom or as indicated clinically.
 
Aggressive management of fluid status and hypotension if present, which could include intravenous fluids and/or diuretics or other blood pressure management, until resolution of CLS sign/symptom or as clinically indicated.
	
Administer 1 mg/kg of methylprednisolone (or an equivalent) per day, until resolution of CLS sign/symptom or as indicated clinically.
 
Aggressive management of fluid status and hypotension if present, which could include intravenous fluids and/or diuretics or other blood pressure management, until resolution of CLS sign/symptom or as clinically indicated.

¹ Tagraxofusp administration may resume in the same cycle if all CLS signs/symptoms have resolved and the patient did not require measures to treat hemodynamic instability. Tagraxofusp administration should be held for the remainder of the cycle if CLS signs/symptoms have not resolved or the patient required measures to treat hemodynamic instability (e.g. required administration of intravenous fluids and/or vasopressors to treat hypotension) (even if resolved), and tagraxofusp administration may only resume in the next cycle if all CLS signs/symptoms have resolved, and the patient is hemodynamically stable.
